106 **IX. Demographic/Patient Specific Data Collected**

107 Age, sex, ASA score, height, weight, body mass index, and comorbidities will be collected.

108 **X. Primary Outcome Measure**

109 - Functional component of the 2012 version KSS at time of consenting and at 3 weeks and 6
 110 weeks following surgery

111 **XI. Secondary Outcome Measures**

112 - A timed up and go (TUG) test before surgery at time of consenting and at 3 weeks and 6
 113 weeks following surgery. The TUG test consists of measuring the time it takes for an
 114 individual to rise from a seated position in a chair, walk to a mark 3 meters away, turn
 115 around, come back, and sit in the same chair from which they started. Patients will be asked
 116 to perform the test twice at each of the aforementioned encounters. The use of any assistive
 117 devices such as cane or a walker) will also be noted.

118 - Occurrence of any of the Knee Society's Standardized List of Complications³¹ (Table 1)

119 **XII. Patients and Protocols**

120 Patients will be enrolled from the clinics of [name] and [name] [name], two
 121 fellowship-trained orthopedic surgeons in the division of Adult Reconstruction at Midwest
 122 Orthopedics at Rush University Medical Center. Study staff will screen the clinic schedule of
 123 each surgeon and will discuss the purposes of the investigation at the time of their visit. If the
 124 patient is willing to participate in the investigation, verbal and written consent will be obtained
 125 by the study staff. At the time of consenting, patients will also be asked to perform a TUG test
 126 and will be asked to complete the questions that comprise the functional component of the KSS
 127 score.

128 This study will be tripled-blinded, thus, the patients, clinicians, and research staff
 129 involved will be unaware of patient allocation during this study. Each patient will receive a study
 130 ID, and a computer randomization system will be used to randomize a list of numerical IDs to
 131 either the treatment or control arm. Study IDs will then be written on medication envelopes, and
 132 a member of the clinical team, who is not involved in this study, will then place either the
 133 treatment drug (Vitamin D) or placebo (empty, opaque gelatin capsule) into the envelopes based
 134 on the ID assignment. Only this clinical team member who is not involved in the study will

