 135 possess the list matching the study ID to the study group assignment, ensuring that the study
 136 remains triple-blinded and that study coordinators are unaware of a patient's assignment when he
 137 or she picks up the study medication.

138 Patients randomized to the experimental arm of the study will receive 50,000IU of
 139 vitamin D₃ before surgery and asked to take the medication orally before surgery. Vitamin D₃
 140 was selected over vitamin D₂ as the former is less expensive and is more effective at raising
 141 serum 25-OH vitamin D levels than the latter.³² The regimen of 50,000IU given once was
 142 selected as this regimen has been previously used without side effects in previous studies and
 143 has been shown to be as effective as other regimens that utilize more frequent dosing with
 144 smaller doses.^{29, 30, 33} Patients randomized to the control arm will receive placebo tablets of
 145 empty, opaque gelatin capsules and advised to consume their medication similar to the
 146 treatment arm. Both groups of patients will receive their medications from the pharmacy at
 147 Rush Medical Center, which will be responsible for providing patients with the appropriate
 148

151 regimen. All patients will receive the same postoperative multimodal analgesic regimen that is
152 normally administered to patients undergoing THA and TKA at Rush University Medical Center.
153

154 In accordance with current standard post-operative care, patients will be asked to follow-
155 up with their surgeon in clinic at 3 weeks and 6 weeks following surgery. At these post-operative
156 visits, patients will be asked to repeat the TUG test and the 19 questions of the functional
157 component of the KSS score.

158 **XIII. Sample Size**

159 Utilizing data from previous studies, an *a priori* power analysis revealed that 45 patients
160 in each cohort are required to detect a minimally clinically important difference (MCID) of 6
161 points in the functional component of the updated, 2012 KSS version with an assumed standard
162 deviation of 10 points. A difference of 6 points was set as the MCID as that is the value found in
163 a previous study evaluating the previous version of the KSS using patient satisfaction and
164 Oxford Knee Scores as anchors.³⁴ To the best of our knowledge, there are no studies that have
165 quantified the MCID for the 2012 KSS yet. Assuming a 10% drop out rate, we will require 50

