166 patients per group for a total of 100 patients overall.

167 **XIV. Treatment and Control Groups**

168 *Numbers reflect an assumed 10% drop out rate

169 Intervention Group: n=50

170 Control Group: n=50

171 **XV. Risks/Benefits**

172 The major risk of patients enrolled in this study stem from potential side effects of
173 hypercalcemia secondary to hypervitaminosis D. Symptoms that have been reported are
174 nausea, dehydration, constipation, polyuria, polydipsia, anorexia, vomiting and muscle
175 weakness. However, documented cases of hypercalcemia due to hypervitaminosis D all involved
176 intake of greater than 40,000IU per day for an extended period of time, and supplementation is
177 widely regarded to be safe in doses under 10,000IU per day for less than 12 weeks^{35, 36}—amounts
178 that are significantly below our proposed dosage. In addition, Binkley et al reported no adverse
179 effects or episodes of toxicity in patients who were supplemented our proposed dosage of
180 50,000IU monthly for one year.³³

181 A risk inherent to every study is the potential for breach of confidentiality and/or
182 privacy. Below is a description of the precautions for maintaining confidentiality.

183 Due to a lack of studies, the benefits of vitamin D supplementation in patients undergoing
184 orthopedic procedures remains unknown. The only study to supplement patients of
185 all vitamin D levels found no differences in functional scores post-operatively among those who
186 did and did not receive supplementation. Based on the many studies demonstrating the negative
187 association between vitamin D deficiency on post-operative outcomes and the benefits of
188 supplementation in patients with knee osteoarthritis, we speculate that supplementation will
189 vitamin D will improve both in patients undergoing total knee arthroplasty with minimal risk of
190 adverse effects.

191 **XVI. Procedures for Maintaining Confidentiality**

192 A breach of confidentiality and/or privacy is a risk of this study. To prevent this, all
193 collected data will be stored electronically in password-protected files to protect patient identity
194 and information. All information will be collected and reviewed by the research team only. Data
195 will be maintained on a password-protected computer that will be accessible only to the study
196 team. No patient identifiers will be maintained in the database.

202
203
204
205
206
207

XVII. Budget

Item	Cost

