11. Periprosthetic fracture	Periprosthetic fracture of the distal femur, proximal tibia, or patella (operative or nonoperative treatment should be recorded).
12. Extensor Mechanism Disruption	Disruption of the extensor mechanism (surgical repair and/or extensor lag should be recorded)
13. Patellofemoral dislocation	Dislocation of the patella from the femoral trochlea (direction of instability should be recorded)
14. Tibiofemoral dislocation	Dislocation of the tibiofemoral joint (direction of instability should be recorded)
15. Bearing surface wear	Wear of the bearing surface symptomatic or requiring reoperation
16. Osteolysis	Expansile lytic lesion adjacent to one of the implants 1 cm in any one dimension or increasing in size on serial radiographs/CT scans

17. Implant loosening	Implant loosening confirmed intraoperatively or identified radiographically as a change in implant position or a progressive, radiolucent line at the bone-cement or bone-implant interface
18. Implant fracture or tibial insert dislocation	Implant fracture or dissociation of the tibial insert from the tibial implant
19. Reoperation	Return to the operating room related to the index TKA (reasons for reoperation should be recorded)
20. Revision	Revision of one or more of the TKA implants (femur, tibia, tibial insert, patella)
21. Readmission	Admission to the hospital for any reason during the first 90 days after TKA (reasons for admission and relation to index TKA should be recorded)
22. Death	Death occurring for any reason during the first 90 days after TKA (cause of death and relation to index TKA should be recorded)

215

216

217

218 **XIX. References**

219 1. Wacker M, Holick M. Vitamin D—effects on skeletal and extraskeletal health and the need for
220 supplementation. *Nutrients*. 2013;5(1):111-48.

221 2. Morrison RJM, Bunn D, Gray WK, Baker PN, White C, Rangan A, et al. VASO (Vitamin D and
222 Arthroplasty Surgery Outcomes) study - supplementation of vitamin D deficiency to improve outcomes
223 after total hip or knee replacement: study protocol for a randomised controlled feasibility trial. *Trials*.
224 2017 Nov 2;18(1):514. Epub 2017/11/04.

225 3. Piuazzi NS, George J, Khlopas A, Klika AK, Mont MA, Muschler GF, et al. High prevalence and
226 seasonal variation of hypovitaminosis D in patients scheduled for lower extremity total joint arthroplasty.
227 *Ann Transl Med*. 2018 Aug;6(16):321. Epub 2018/10/27.

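### Section XII does not stratify allocation by surgeon or state how the list is restricted, so surgeon balance is left to chance; stratifying and adjusting costs almost nothing

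*Combined protocol and SAP*

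**What the plan says.** Section XII recruits from the clinics of two "fellowship-trained orthopedic surgeons in the division of Adult Reconstruction at Midwest" Orthopedics, at one centre. Allocation is described once: each patient receives a study "ID, and a computer randomization system will be used to randomize a list of numerical IDs to" "either the treatment or control arm. Study IDs will then be written on medication envelopes, and" the envelopes are filled by someone outside the study. The text mentions no ratio, blocks or strata.

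Section XIV plans "Intervention Group: n=50" and the same number of controls. The Section XVII budget covers 50 patients' supply of each product.

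Section IX states that "Age, sex, ASA score, height, weight, body mass index, and comorbidities will be collected". Surgeon is not in that list. No section sets out an analysis model, so nothing adjusts for surgeon.

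Under Section XII, patients return to their own surgeon's clinic at 3 and 6 weeks, where the KSS functional component and the TUG are repeated.

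**The concern.** Surgeon identifies both who operates and the clinic where the primary outcome is collected, so it could plausibly explain some of the spread in early function. The plan protects against chance imbalance on it neither by design nor by analysis. With about 45 evaluable patients per arm, a noticeable difference in surgeon mix between arms is not rare. If the surgeons' patients differ in mean KSS, that difference adds noise to the treatment comparison. The noise can be removed almost for free, and an unexplained imbalance would invite questions when the result is read.

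**Working it through.** **1. The plan's own figure.** Section XIII gives a difference of 6, an SD of 10, 45 evaluable per arm and 10% drop-out. Alpha, sidedness and power are not stated; two-sided 5% and 80% are assumed. The two-sample t-test then needs 44.6, rounded up to 45 per arm, and 45/0.9 = 50. The plan's numbers reproduce.

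Power at 45 per arm: standard error = 10 × √(2/45) = 2.108; 6/2.108 = 2.846; with 88 degrees of freedom, power = 80.4%.

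**2. Surgeon balance if the list is fixed at 50/50.** This is the reading most favourable to the plan. Let *m* of the 100 patients belong to surgeon A and *h* of those fall in the vitamin D arm. Then *h* is hypergeometric (100, *m*, 50), and the difference in surgeon share is h/50 − (m − h)/50 = (2h − m)/50. The documents do not give surgeon volumes, so a range is shown.

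| Assumed volumes | SD of difference | Gap ≥ 10 points | Gap ≥ 20 points |
|---|---|---|---|
| 50:50 | 0.101 | 32% | 7% |
| 60:40 | 0.098 | 31% | 7% |
| 70:30 | 0.092 | 28% | 5% |
| 80:20 | 0.080 | 21% | 2% |

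For example, at 50:50 a gap of 10 or more points needs h ≤ 22 or h ≥ 28. Had allocation been simple randomisation, the 10-point figures would be 37% at 50:50 and 21% at 80:20, so the conclusion does not depend on which method is meant.

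**3. What a gap does to the estimate.** If the surgeons' mean KSS differs by D, the chance shift has SD D × 0.1005 at equal volumes. For an assumed D = 5 this is 0.50, a 95% range of ±1.96 × 0.50 = ±1.0 point. Total sampling error is ±1.96 × 2.108 = ±4.1 points. If the SD of 10 describes all patients of both surgeons, the first is already contained in the second.

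**4. What removing it gains.** Hold the total SD at 10 with equal volumes. The between-surgeon variance is 0.5 × 0.5 × D² = 0.25D², so the SD within surgeon is √(100 − 0.25D²). Power uses 45 per arm and 87 degrees of freedom.

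| Assumed D | SD within surgeon | Power |
|---|---|---|
| 0 | 10.00 | 80.4% |
| 3 | √97.75 = 9.89 | 81.2% |
| 5 | √93.75 = 9.68 | 82.8% |
| 8 | √84 = 9.17 | 86.7% |

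The row D = 0 shows the cost of the extra model term: 80.36% against 80.37%. At 80:20 the gain is smaller: for D = 5 the variance removed is 0.16 × 25 = 4.0 rather than 6.25.

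**5. Unequal arm totals.** After 10% drop-out, power is 80.0% at 45:55 (40.5 and 49.5 evaluable) and 78.8% at 40:60 (36 and 54), against 80.4% at 50:50. Arm size is therefore not where the benefit lies.

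**The case against.** The strongest reply is that this is mostly a gap in description. A reader might infer from Section XII that the list is unrestricted and that the planned 50:50 split will therefore fail. The documents do not support that. Section XII is silent on restriction, and the 50 and 50 in Section XIV, with product budgeted for 50 patients each, fit a list shuffled to exactly 50 per arm. Even if the split did drift, step 5 shows a cost of under 2 points of power at 40:60. This part of the objection stands.

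It is also fair that no surgeon effect on KSS is given anywhere. The two surgeons work in one division, and all patients receive the same analgesic regimen. Chance imbalance is random error already inside the planned SD, so calling it bias would be wrong. Most of the precision gain comes from adjusting for surgeon, which does not need separate lists.

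Other stronger readings fail as well. That surgeon could not be adjusted for goes too far: staff screen each surgeon's schedule, so surgeon is known at enrolment even though Section IX omits it. That season needs balancing would rest on the title of reference 3, "seasonal variation of hypovitaminosis D in patients scheduled for lower extremity total joint arthroplasty"; no section links season to KSS at 3 or 6 weeks.

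What the objection does not remove: under either reading of the list, surgeon balance is left to chance, and no planned analysis recovers the lost precision.

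**Conclusion.** The point holds as a cheap improvement in design and analysis, not as a flaw that threatens validity. The described method leaves a gap in surgeon share of 10 or more points in about 32% of lists at equal volumes and 21% at 80:20, even with totals fixed at 50/50. Stratifying and adjusting would raise power from 80.4% to about 81%, 83% or 87% for surgeon differences of 3, 5 or 8 KSS points.

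These figures rest on assumed volumes and surgeon differences, an SD of 10 taken as the total across both surgeons, and an unstated but reproducible two-sided 5% test. If the surgeons do not differ, nothing is gained and practically nothing is lost.

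**What to change.** - **Section XII:** state a 1:1 ratio and randomise separately within each surgeon, in permuted blocks of varying size (for example 4 and 6) concealed from study staff.
- **Section IX:** add surgeon to the recorded data.
- **Analysis:** include surgeon as a fixed factor in the KSS and TUG comparisons.

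The cost is a second envelope series, one degree of freedom and slightly more predictable allocation, which the varying block sizes and the blinding limit. The sample size stays at 100. With blocks no larger than 6, an unfinished block can put the arms at most 3 apart within a surgeon, so at most 6 apart overall, or 47:53. That also secures near-equal arms if recruitment stops early, which a list fixed only at 50/50 overall would not.

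### Cheap improvement: Section XII promises patient blinding but specifies an empty gelatin capsule as placebo and never says that the active and placebo units match

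*Combined protocol and SAP*

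**What the plan says.** **Blinding claim.** Section XII (Patients and Protocols) opens its blinding paragraph with "This study will be tripled-blinded, thus, the patients, clinicians, and research staff" and goes on to say that these groups will not know the allocation.

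**How blinding is to be achieved.** Study IDs are randomized by computer and written on envelopes. Then "a member of the clinical team, who is not involved in this study, will then place either the" "treatment drug (Vitamin D) or placebo (empty, opaque gelatin capsule) into the envelopes based" on the ID assignment. The section adds "Only this clinical team member who is not involved in the study will" hold the list that links ID to arm, and it presents this as what keeps the study triple-blinded.

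**The placebo.** It is described as empty in three places: the envelope-filling sentence above; the control-arm sentence, "Patients randomized to the control arm will receive placebo tablets of" "empty, opaque gelatin capsules and advised to consume their medication similar to the" treatment arm; and the placebo line of the Section XVII budget, which also calls the gelatin product a tablet.

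**The active.** In the envelope-filling sentence it is only named as vitamin D. Its physical form appears once, in the budget, as a 50,000 IU tablet.

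**Supply.** Section XII also says "Both groups of patients will receive their medications from the pharmacy at" "Rush Medical Center, which will be responsible for providing patients with the appropriate" regimen.

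**Primary outcome.** Section X makes it the functional component of the 2012 KSS, measured at consent and at 3 and 6 weeks. Section XII describes this as 19 questions that the patient answers.

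**The concern.** Blinding has two parts: hiding the assignment list, and making the two products indistinguishable to the person who takes them. Section XII covers the first part and is silent on the second. An opaque shell hides its contents from sight, but it does not deal with weight or feel, and a control patient may notice that a capsule is empty. Nothing in the protocol prevents that, and as written it directs that controls receive an empty shell.

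This matters because of the endpoint. Section IV describes the functional KSS as an objective measure, but it consists of the patient's own answers. If some control patients conclude that they had placebo and rate their function lower, the KSS difference moves in favour of vitamin D, and the KSS data alone cannot separate that shift from a drug effect. The timed TUG at the same visits is a partial cross-check, but it is a secondary outcome and depends on effort. The gap is easy to close before enrolment and cannot be repaired once the single dose has been taken.

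**Working it through.** **1. What the text secures, and for whom.**

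- Clinicians and study staff: coded envelopes, a packer outside the study, and a list held by that person alone. Allocation is concealed.
- Patients: the same envelopes, plus the word *opaque* for the placebo shell. There is no statement on form, size, colour, weight, marking, fill or over-encapsulation.
- Form of the active: *tablet*, in the budget only. The same budget and the control-arm sentence also use *tablet* for the gelatin placebo, so the word does not tell the products apart and the form of the active is unsettled.

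**2. The plan's own sample size.** Section XIII gives a 6-point difference, SD 10, 45 per arm, 10% dropout and 50 enrolled per arm. It states neither alpha nor power; two-sided 5% and 80% are assumed here.

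- Normal approximation: n = 2 × (1.960 + 0.842)² × 10² / 6² = 43.6, so 44.
- Two-sample t-test: 44.6, so 45, which matches the plan.
- Dropout: 45 / 0.90 = 50, which matches.
- Variants that do not fit (normal approximation): a one-sided test gives 35, and 90% power gives 59.

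The point about matching changes none of these figures.

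**3. Precision of the comparison.** SE = 10 × √(2/45) = 2.11 points.

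**4. What an assumed bias would do.** The documents give no bias size, so this step is illustration only. Suppose there is no drug effect and only control patients shift. Those who guess correctly score lower, and those who guess wrongly score higher by the same amount:

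net bias b = shift × (fraction right − fraction wrong)

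Two-sided 5% rejection rate = Φ(b/SE − 1.96) + Φ(−b/SE − 1.96)

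| Assumed shift (points) | Net fraction of controls | Net bias b | False-positive rate |
|---|---|---|---|
| none | – | 0 | 5.0% |
| 1 | 0.25 | 0.25 | 5.2% |
| 2 | 0.50 − 0.25 = 0.25 | 0.5 | 5.6% |
| 3 | 0.25 | 0.75 | 6.5% |
| 2 | 0.50 | 1.0 | 7.6% |
| 3 | 0.50 | 1.5 | 11.0% |

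Doubling the error rate to 10% needs b of about 1.38 points, for example a net 1.375/2 = 69% of controls each shifting 2 points. If right and wrong guesses are equally common, b = 0 and there is no bias. A mean bias of 3 points would give 29.6%, but that needs, for example, a net half of controls each shifting by 6 points, the plan's full MCID.

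**5. Cost on the plan's own prices (Section XVII).** Current total: 17.40 + 5.69 = $23.09. Placebo shells: 5.69/50 = about $0.114 each. With 50 more shells at that price: 17.40 + 2 × 5.69 = $28.78.

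**The case against.** The strongest reply is that recognition is unlikely. The regimen is one dose, taken once, from one coded envelope, and nothing in the protocol has a patient see the other arm's product. A patient would have to notice that a single opaque capsule is empty, infer placebo, and let that belief colour answers 3 and 6 weeks later, after a knee replacement. This stands, and it lowers the probability of bias considerably. It does not remove the gap, because noticing that a capsule is empty needs no comparator.

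A reader might infer from the budget that a tablet is being compared with a capsule. The documents do not support that. The word *tablet* is applied to both products, and the active may already be in a matching shell. The lack of an over-encapsulation line in a two-item budget is no evidence either, since none would be needed in that case.

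A reader might also see a contradiction over who holds the allocation list, because the pharmacy is made responsible for providing the regimen. That does not hold. Section XII says that only the uninvolved team member has the list, and envelopes already filled and labelled by ID can be handed out without it. The division of labour could be clearer, but the question of the list is answered.

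Finally, the bias figures are assumptions. That is correct, and the case for the change does not rest on them.

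**Conclusion.** The point holds as a correctable weakness in the specification. The protocol promises patient blinding, directs that controls receive an empty gelatin capsule, and does not say that the units match, while the primary outcome is answered by the patient. A filled, matched placebo is plainly better than the one described and costs little.

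It would go too far to conclude that patient blinding is broken or that the KSS result will be biased. That an empty shell may be recognised is an inference, and the units may match in practice.

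On size, the illustrated range is 5.2% to 11.0% false positives for net biases of 0.25 to 1.5 points. It rests on assumed shifts of 1 to 3 points, a net 25% to 50% of controls shifting, no shift in the vitamin D arm, 45 evaluable per arm, SD 10 and a single two-sided 5% test. The effect is probably small unless recognition is common. The change is recommended because it is cheap and can only be made before dosing, not because a large bias has been shown.

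**What to change.** In Section XII, state the dosage form and appearance of the vitamin D3 unit, and replace the empty capsule with wording such as:

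*The placebo will be indistinguishable from the vitamin D3 unit in appearance, weight and feel, for example the same opaque gelatin shell with an inert fill. The active will be over-encapsulated only if it is not already supplied in that shell.*

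Use one product description in the envelope-filling sentence, the control-arm sentence and the Section XVII budget, so that tablet and capsule are no longer mixed.

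Optionally, add a sentence that the pharmacy supplies the product or dispenses the coded envelopes while the uninvolved team member fills them, if that is the intended arrangement. Nothing needs adding about the list.

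**Cost.** Inert filler and preparation time, which the documents do not price. If the active is already in a matching shell, the product cost is $23.09 plus filler. If over-encapsulation is needed, 50 more shells add about $5.69, for $28.78 plus filler, assuming they cost the same as the current placebo shells. Dose, visits and sample size do not change.

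### The protocol body plans no collection of the hypercalcemia symptoms it names as the major risk, short of readmission or death, so there would be no planned by-arm data on milder harms

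*Combined protocol and SAP*

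**What the plan says.** Section XV (Risks/Benefits) states: "The major risk of patients enrolled in this study stem from potential side effects of" hypercalcemia caused by too much vitamin D. The symptoms it gives are "nausea, dehydration, constipation, polyuria, polydipsia, anorexia, vomiting and muscle" weakness, eight in all. It then offers reassurance. Documented cases are said all to have involved "intake of greater than 40,000IU per day for an extended period of time", and one cited study is said to have found no adverse "effects or episodes of toxicity in patients who were supplemented our proposed dosage of" "50,000IU monthly for one year".

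The outcomes are set out elsewhere. Section X gives the functional component of the 2012 Knee Society Score (KSS). Section XI adds the timed up and go (TUG) test and the Knee Society's "Standardized List of Complications", which is reproduced as Table 1 with 22 items. For the 3- and 6-week visits, Section XII says that at these "visits, patients will be asked to repeat the TUG test and the 19 questions of the functional" component of the KSS. Section IX adds demographic data and comorbidities.

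**The concern.** The protocol identifies a harm, ranks it first and describes how it would show itself, but the schedule never asks about it. The complication list was written for knee replacement surgery, not for an oral vitamin D dose, so it is not a natural place for these symptoms to appear.

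What is at stake is the safety statement that the trial can make at the end. Section XV expects little risk from supplementation. Below the level of readmission or death, the trial would have no planned comparison between arms to set beside that expectation. Symptoms that nobody asked about at 3 and 6 weeks cannot be recovered systematically at analysis. The efficacy question is not touched.

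**Working it through.** **1. Is any of the eight symptoms collected?** Each data-collection statement was set against the Section XV list.

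| Place | What is collected | Any of the eight symptoms? |
|---|---|---|
| Section IX | Demographics, ASA score, body size, comorbidities | No |
| Section X | KSS functional component | No |
| Section XI | TUG, assistive devices, Table 1 complications | Only through Table 1 |
| Section XII, 3- and 6-week visits | TUG and 19 KSS questions | No |
| Table 1, items 1–20 | Surgical and implant events, reoperation, revision | No |
| Table 1, items 21–22 | All-cause readmission and death to 90 days, with reasons | Only if that serious |

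So 0 of 22 Table 1 items name a symptom, and 2 of 22 would capture serious cases. Item 4 is the nearest other entry, but it is a neural deficit attributed to the index knee replacement, not muscle weakness from raised calcium. Calcium appears in the protocol only in eligibility (Section VIII) and background. No post-operative measurement is planned.

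**2. How likely are events?** The protocol's own evidence points to few. If the cited monthly regimen means 12 doses in the year (an assumption), that is 12 × 50,000 = 600,000 IU, against a single 50,000 IU here: 600,000 / 50,000 = 12 times as much.

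**3. How many patients would there be?** Section XIII gives 45 per arm, for a 6-point difference and a standard deviation of 10. Assuming two-sided 5% significance and 80% power, which the protocol does not state, the normal approximation gives 44 per arm and the t-test 44.6, so 45 reproduces. With 10% dropout, 45 / 0.90 = 50 per arm. These figures serve only as the denominators below.

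**4. What could a symptom question show?** The protocol gives no symptom rates, so 10%, 20% and 30% in both arms are assumed. The half-width of a 95% confidence interval for the difference is 1.96 × √(2p(1 − p)/n).

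| Assumed rate p | n = 45 per arm | n = 50 per arm |
|---|---|---|
| 10% | 1.96 × √(0.18/45) = 12.4 points | 1.96 × √(0.18/50) = 11.8 points |
| 20% | 1.96 × √(0.32/45) = 16.5 points | 1.96 × √(0.32/50) = 15.7 points |
| 30% | 1.96 × √(0.42/45) = 18.9 points | 1.96 × √(0.42/50) = 18.0 points |

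These widths do not measure the gap. They show why the added data should be counts and not comparisons by test.

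**The case against.** The strongest reply is that little is lost. There is one dose. Section VIII excludes renal disease, past hypercalcemia, malabsorption and other vitamin D or calcium use. The purpose and hypothesis concern function, and the remark about low risk is offered as speculation, not as a planned claim. Serious cases are already recorded. Weakness that limits mobility could show in TUG and KSS, although not as an identifiable harm. Patients see their surgeon at 3 and 6 weeks anyway, so a notable symptom may reach the chart. All of this stands, and it is why the point is minor.

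It is also true that the added data would be hard to read. Section XII says "All patients will receive the same postoperative multimodal analgesic regimen that is" usual at the center, and nausea, vomiting and constipation are to be expected on such a regimen after surgery. Without calcium measurements no symptom could be put down to hypercalcemia. Without a baseline question, pre-existing complaints would be counted too. Randomization and the placebo arm help, because both arms share this background, but they do not make the counts precise.

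What the reply does not remove is the absence of any plan to ask. Chart entries depend on who happens to mention or write down what, and the protocol has no procedure for extracting or tabulating them.

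A reader might infer two stronger things. One is that harms cannot be reported by arm at all. The documents do not support that: readmissions and deaths would be available with reasons, and spontaneous reports may exist. The other is that the dose is unsafe, since Section XV cites 40,000 and 10,000 IU per day and describes them as below the trial dose. One 50,000 IU dose does exceed both figures, but those are daily amounts and the documented cases followed extended intake. Averaged over the 42 days to the last visit, the dose is 50,000 / 42 ≈ 1,190 IU per day. An average is not the same as a bolus, but nothing in the protocol shows danger from this dose.

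**Conclusion.** The concern holds as a minor gap in safety data collection. The protocol body names eight symptoms as the expression of its major risk and plans to collect none of them unless they lead to readmission or death. Below that level there would be no planned by-arm data.

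This rests on a reading of the protocol body. The consent pages were not available, and spontaneous or chart-based reports are possible. It does not rest on events being likely; the protocol gives good grounds to expect few. No efficacy conclusion, primary analysis or sample size depends on it. The case for acting is that the remedy is cheap and the information cannot be gathered systematically once the visits have passed.

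**What to change.** Add to Section XI a short adverse-event question, asked by blinded staff at the 3- and 6-week visits. List in plain language the Section XV symptoms that a patient can report: nausea, vomiting, constipation, loss of appetite, unusual thirst, passing more urine than usual, and muscle weakness. Dehydration is hard to self-report and can fall under an open item for any other problem. Ask about the time since surgery at 3 weeks, and since the last visit at 6 weeks.

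Report by arm the number of patients with each symptom at either visit and with any symptom, descriptively and without hypothesis tests. List any hypercalcemia found in routine care as individual cases, because only patients tested for clinical reasons would be seen and there is no proper denominator.

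The cost is a few questions at two visits that already take place, with no new visit, test or staff. The limits should be stated with the results: non-specific symptoms after surgery with analgesics, recall over about three weeks, no attribution to hypercalcemia without calcium measurement, and imprecise arm differences with 45 to 50 patients per arm.
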